10.3.2 Secondary Objectives

To evaluate the bio-distribution of NU-0129 in tumor tissue we will provide descriptive statistics regarding intensity of concentration of particles in various parts of tumor tissue.

To evaluate the pharmacokinetics of NU-0129 in blood samples collected at 1, 3, 5, 10, 30, 60 minutes and 4, 8, and 24 hours post-dose, we will provide appropriate pharmacokinetic curves and parameters such as Cmax, Tmax etc.

To evaluate the feasibility of NU-0129 administration, we will record a) successes/failures, b) number of attempts to administrate nanoparticles.

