Group Number	Test Article	Dose Level	Dose Volume	Number of Animals	
		(mg/kg)	(mL/kg)	Males	Females
1	Vehicle	0	5	5	5
2	NU-0129	1	5	5	5
3	NU-0129	4	5	5	5
4	NU-0129	8	5	5	5

*The dose levels correspond to the amount of siRNA, the actual test article component, in the neat powdered material.

On the day of dosing, blood samples were collected from all animals prior to dosing and at approximately 3, 10, and 30 minutes, and 2, 8, and 24 hours post-dose. Plasma was analyzed for the concentration of NU-0129 using liquid chromatography with FLD. The results of these analyses were used for toxicokinetic analysis.

The toxicokinetic parameters for NU-0129 in plasma are summarized in Table T2.

Table T2. Toxicokinetic Parameters for NU-0129 in Male and Female Monkeys

Dosage (mg/kg)	Males						Females					
	1		4		8		1		4		8	
	Mean	SD	Mean	SD	Mean	SD	Mean	SD	Mean	SD	Mean	SD
AUC _{last} (µg*h/mL)	0.232 ^{†1}	NA	2.37	1.04	9.82	2.82	0.321 ^{†3}	0.10	3.62	0.71	14.2	1.90
C ₀ (µg/mL)	1.67	0.879	34.0	19.8	131	51.4	3.90	2.31	68.9	18.1	174	36.3
T _{1/2} (h)	NC	NA	0.06	0.00	0.08	0.04	0.05 ^{†3}	0.00	0.05	0.00	0.07	0.01
Cl (mL/h/kg)	NC	NA	1980	863	863	224	3340 ^{†3}	1070	1140	250	570	93.2
V _{ss} (mL/kg)	NC	NA	158	86.7	72.6	26.0	213 ^{†3}	75.3	66.1	22.4	50.2	7.52

N = 5, except where designated with [†]N

Following a single IV bolus dose of NU-0129 to male and female monkeys, exposure increased with increasing dose. The increase in AUC_{last} was greater than dose proportional as NU-0129 dose increased from 1 mg/kg to 8 mg/kg. NU-0129 exposure, in terms of AUC_{last}, was slightly higher in females than in males, but differences were <2-fold.

Clearance, V_{ss}, and terminal half-life were not calculable at 1 mg/kg for males. Mean Clearance, ranging from approximately 600 to 3000 mL/h/kg, was moderate to high (approximately 20% to 120% of hepatic blood flow in the monkey as reported by Davies and Morris, 1993) and decreased as dose increased. Mean V_{ss} was small, ranging from approximately 50 to 200 mL/kg (approximately 10% to 30% of total body water in the monkey as reported by Davies and Morris, 1993) and also decreased with increasing dose. This resulted in a short terminal elimination halflife that ranged from approximately 2 to 9 minutes for individual animals. Clearance- and V_{ss} values were approximately 1.4- to 2-fold higher for males than females, but half-life values were similar.

1.2.2 **Pre-clinical toxicity studies**

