4.2 NU-0129 Administration

Patients will be admitted for a one-time administration of IV NU-0129 at a nominal dose of 0.04mg/kg (approximately 0.03 to 0.05mg/kg), based on the patient's weight at screening. Patients will be dosed based on total body weight and the resulting dose will be rounded to one of the 5 dose groups as shown in dosing chart below.

Patient's weight in kg	Dose in mg (Oligonucleotide component)	Corresponding dose (mg/kg)
Up to 37.0 kg	0.987 mg	Up to 0.027
≥ 37.0 to < 61.7 kg	1.974 mg	0.053 to 0.032
≥ 61.7 to < 86.4 kg	2.96 mg	0.048 to 0.034
≥ 86.4 to < 111.0 kg	3.95 mg	0.046 to 0.036
≥ 111.0 to 135.7 kg	4.94 mg	0.045 to 0.036

The infusion rate will be 5.0-8.0 mL/minute over approximately 20 - 50 minutes. The flow rate will be monitored closely and the tissue surrounding the catheter examined frequently for any signs of extravasation. Patients will be monitored with telemetry from the beginning of the infusion for at least 8 hours post-infusion. Thereafter, vitals will be monitored at least every 4 hours for a total of 24 hours from the end of infusion.

Immediately after the infusion is completed, PK blood draws will take place at 1, 3, 5, 10, 30, and 60 minutes (± 1 minute) post-dose as well as 4, 8 and 24 hours (± 5 minutes)

post-dose. If necessary, blood draws may take place during the patient's resection surgery, however this should be avoided when possible.

Patients will remain inpatient for a tumor resection, occurring 8-48 hours after treatment with NU-0129. Vitals will be measured continuously throughout the surgery. Standard of care post-operative procedures will take place per institutional guidelines, including a brain MRI within 48 hours after the resection. Physician determined response will be determined using RANO (Response assessment in neurology-oncology) criteria. (NOTE: patient response is not expected based on a single sub-therapeutic dosing. In addition, the surgery may confound response assessment.)

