6.3 Secondary Endpoints

6.3.1 Pharmacokinetics

PK blood samples will be collected post-infusion at 1, 3, 5, 10, 30, and 60 minutes (+/- 1 minute), and 4, 8, and 24 hours (+/- 5 minutes).

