8.1.11 Nursing implications

The dose (based on dosing chart) will be based on the patient's weight at baseline. The infusion rate will be 5.0-8.0 mL/minute. A sterile, non-pyrogenic, low-protein binding 0.22 μ m in-line filter must be used during administration to remove any adventitious particles. If the infusion set does not contain in-line filter, 0.22 μ m add-on filter should be used. The flow rate will be monitored closely and the tissue surrounding the catheter examined frequently for any signs of extravasation.

Drug Administration Log should be completed by administering nurse and returned to study coordinator, documenting date and time of infusion start/ stop, interruptions (if any). Any staining or discoloration of the syringe, IV bag, delivery device, and /or administration set should be documented in the Administration Log.

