9.1 Blood Sample Collection Guidelines

Blood samples will be collected for PK analysis at 1, 3, 5, 10, 30, and 60 minutes (\pm 1 minute), and 4 hours, 8 hours, and 24 hours (\pm 5 minutes) post NU-0129 infusion. Each sample will contain 1mL of blood collected in pre-chilled 4mL K2EDTA tubes and maintained on wet ice throughout collection and processing. See separate lab manual for full collection and processing details.

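### All PK samples follow the end of infusion, so the planned Tmax carries no drug information and the observed Cmax reads below the true peak by a timing-dependent amount

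*Combined protocol and SAP*

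**What the plan says.** Section 4.2 sets the infusion: "The infusion rate will be 5.0-8.0 mL/minute over approximately 20 - 50 minutes". It then fixes the sampling clock: "Immediately after the infusion is completed, PK blood draws will take place at 1, 3, 5, 10, 30, and 60 minutes", each within 1 minute either way, followed by draws at 4, 8 and 24 hours within 5 minutes. Section 6.3.1 agrees: "PK blood samples will be collected post-infusion at 1, 3, 5, 10, 30, and 60 minutes". Sections 2.2.1 and 9.1 and the footnotes to Table 5.1 give the same nine times. The study summary and section 10.3.2 use the looser term post-dose, which section 4.2 settles. No draw is listed before, during or exactly at the end of the infusion.

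For analysis, section 10.3.2 states "we will provide appropriate pharmacokinetic curves and parameters such as Cmax, Tmax etc". It does not define time zero for Tmax, say whether nominal or actual times are used, or say how the level at the end of infusion is obtained. It does not name AUC or clearance.

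Section 1.2.1 gives the only half-life in the documents, from monkeys given an intravenous bolus: a "short terminal elimination halflife that ranged from approximately 2 to 9 minutes" in individual animals. Section 8.1.11 requires a log of infusion start and stop times and any interruptions.

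**The concern.** Tmax and Cmax are the only two parameters that the plan names. Both are usually read straight off the observed profile, and here that profile begins after the peak. A tabulated Tmax would look like a finding about the drug but would reflect when the pump stopped and when the nurse drew blood. A tabulated Cmax would mix true differences between patients with differences in draw time of a minute or two. With 6 to 8 patients, that artefact could pass for biological variability. If AUC or clearance is added under the open end of the list, the infusion phase would have to be filled in by some rule, and none is stated.

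**Working it through.** **Inputs.** Infusion duration T = 20 to 50 min (section 4.2). First draw nominally 1 min after the end, so 0 to 2 min with the window (sections 4.2, 6.3.1). Half-life h = 2 to 9 min (section 1.2.1); the Table T2 means of 0.05 to 0.08 h are 3.0 to 4.8 min and fall inside that range. No human half-life is given, so h = 60 min is added as an assumed contrast.

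**Reproducing the stated duration.** Each vial is made up in 1 mL and diluted 1:50 (section 8.1.6), so about 50 mL per vial. At 5.0 mL/min, two to five vials take 100/5 = 20, 150/5 = 30, 200/5 = 40 and 250/5 = 50 min, which matches section 4.2. At 8.0 mL/min, two vials take 100/8 = 12.5 min.

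**Tmax.** With a constant input rate and elimination rate k = ln2/h, the level during infusion is proportional to 1 − exp(−kt). It rises until t = T and then falls as exp(−k × time since stop). This holds for every k. The largest observed value is therefore expected at the first draw: about 1 min counted from the end of infusion, or T + 1 min counted from its start.

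**Cmax.** Observed/true = exp(−k × delay) = 2^(−delay/h). For h = 2: 2^(−1/2) = 0.71 at 1 min and 2^(−1) = 0.50 at 2 min. For h = 9: 2^(−1/9) = 0.93 and 2^(−2/9) = 0.86. A draw at 0 min loses nothing. At h = 2, two patients with the same peak drawn at 0 and 2 min would differ by 1/0.50 = 2-fold.

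**AUC, if reported (one compartment).** Share before the first draw at 1 min = 1 − exp(−k) × (1 − exp(−kT))/(kT), with k per minute. For T = 20, h = 9: k = 0.0770, kT = 1.540, and 1 − 0.926 × 0.786/1.540 = 0.53. For T = 50, h = 2: k = 0.347, kT = 17.3, and 1 − 0.707 × 1.000/17.3 = 0.96.

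A plain trapezoid takes zero at infusion start, a straight line to the 1-minute sample, and exact decline afterwards. Its ratio to the true AUC is exp(−k) × (1 − exp(−kT)) × [(T+1)/(2T) + 1/(kT)].

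| h (min) | Cmax ratio at 1 min | Cmax ratio at 2 min | AUC before first draw, T=20 / T=50 | Trapezoid/true AUC, T=20 / T=50 |
|---|---|---|---|---|
| 2 | 0.71 | 0.50 | 90% / 96% | 0.47 / 0.40 |
| 3 | 0.79 | 0.63 | 83% / 93% | 0.58 / 0.47 |
| 4.8 | 0.87 | 0.75 | 72% / 88% | 0.71 / 0.56 |
| 9 | 0.93 | 0.86 | 53% / 76% | 0.85 / 0.70 |
| 60 (assumed) | 0.99 | 0.98 | 12% / 25% | 0.99 / 0.97 |

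Half of the AUC precedes the first draw at h = 9.8 min for T = 20 and at h = 22.9 min for T = 50; for longer half-lives the share is below half. With a 12.5-minute infusion the share is 41-84% for h = 9 down to 2.

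**The case against.** Section 2.2.1 sets a narrow aim: concentrations at stated times after administration. The nine draws deliver that. Tmax is uninformative for any constant-rate intravenous infusion, so sampling during the infusion would not rescue it. The Cmax loss is zero for a draw at 0 min, and the draws at 1, 3, 5 and 10 min allow back-extrapolation. The half-life comes from monkeys given a bolus of 1 to 8 mg/kg, with AUC rising more than in proportion to dose; patients receive about 0.04 mg/kg by infusion. The human assay is described only in a separate lab manual. No decision rule uses PK: under section 4.3, future dosing rests on safety review by the DSMB.

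Most of this stands, and it limits the size of the point. It does not explain why Tmax is listed as a result, and the plan does not say that back-extrapolation will be done.

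A reader might go further and infer that most of the exposure will be lost, or that AUC will be understated and clearance overstated. The documents do not support that. They plan neither parameter. The share of AUC before the first draw is also not the share lost: even a plain trapezoid recovers 40-85% at the monkey half-lives, and the logged infusion times permit a model-based estimate. A reader might also infer that the monkey schedule was carried over to patients. No section says so, and the schedules differ: monkeys were sampled before dosing, and patients have additional early draws at 1 and 5 min.

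**Conclusion.** The point holds for the two named parameters. Tmax as planned carries no drug information, for any half-life, given a constant infusion rate. Observed Cmax is biased downward whenever the first draw comes after the infusion stops. The size of that bias is conditional on half-life: 7-29% at the nominal draw and 0-50% across the window if the monkey range of 2 to 9 min applies, but about 1% at 1 minute if the half-life is 60 min.

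The AUC part is doubly conditional: on AUC or clearance being reported at all, and on a short half-life with one-compartment decline. Under those conditions 53-96% of AUC precedes the first draw for infusions of 20 to 50 min, against 12-25% at 60 min. What is missing there is a stated estimation method, not data that cannot be recovered.

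This is a gap in the analysis of a descriptive secondary objective. It should be corrected, but it does not touch the primary safety endpoint.

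**What to change.** Amend section 10.3.2 as follows.

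- Do not report Tmax as a result.
- Report the end-of-infusion concentration, back-extrapolated on the log scale from the 1, 3, 5 and 10 minute samples to the logged stop time, using actual draw times. Show the observed first-sample value and its actual time beside it. Where too few of these samples are quantifiable to fit a line, report the observed value only and say so.
- If AUC or clearance is reported, estimate it with zero-order input over the logged start and stop times, allowing for logged interruptions, and label the infusion-phase part as model-based.

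The cost is a few sentences and a little modelling. No sample is added or moved; moving late draws into the infusion would thin the information on any longer terminal phase and is not part of this proposal. The main downside is that the model-based part is uncertain, because the monkey data show non-linear kinetics and the human decline may not follow a single exponential. Stating the model before the data are seen, and giving the observed values alongside, keeps that uncertainty visible.

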Objectives	
Primary Objective:
 
 • To evaluate the safety of NU-0129 SNA gold nanoparticle infusion in patients with recurrent GBM or GS 
Secondary Objectives:
 
 • To evaluate the bio-distribution of NU-0129 in tumor tissue • To evaluate the pharmacokinetics of NU-0129 in blood samples collected at 1, 3, 5, 10, 30, 60 minutes and 4, 8, and 24 hours post-dose • To evaluate the feasibility of NU-0129 administration 
Exploratory Objectives
 
 • To evaluate the Bcl2L12 expression levels and apoptotic markers in the tumor tissue post-treatment • To evaluate preliminary response (Overall Survival and Progression Free Survival at 2 years, as well as Overall Response Rate)
Sample Size	6-8 patients will be enrolled
Diagnosis & Key Eligibility Criteria	
 • Patients should have a diagnosis of recurrent glioblastoma multiforme (GBM) or gliosarcoma (GS) after failing prior therapy. • Eligible patients must be surgical candidates where surgery is felt to be an appropriate treatment option. • Bone marrow and organ function must be adequate as defined below 
 • WBC \geq 3,000/μL • ANC \geq 1,500/mm³ • Platelet count of \geq 100,000/mm³ • Hemoglobin \geq 8 g/dL • Bilirubin \leq 2 x ULN • AST/ALT \leq 2 x ULN • Creatinine \leq 1.5 x ULN 
Patients must not have had prior cancer therapy (including biologic, cytotoxic, and experimental therapies and nitrosoureas) within 21 days of registration.

Treatment Plan	Once registered, eligible patients will receive intravenous NU-0129 nominal dose \sim 0.04mg/kg (based on dosing chart) one time. Patients will be monitored with telemetry, vital signs, and labs before, during and after the infusion as indicated in section 5.0. Treatment will be followed by a tumor resection 8-48 hours later. The tissue will be collected and analyzed for bio-distribution and exploratory studies.

NU Study Number: NU 16C01

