2.2.3 Feasibility

- To assess the feasibility of giving NU-0129 as a standard treatment for recurrent GBM or GS.
- Feasibility will be calculated as the rate of successful production, delivery, and administration of the investigational product and subsequent resection.

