4.9 Patient Replacement

If a patient withdraws for any reason after consent or registration but before receiving investigational product, he or she may be replaced.

If a patient receives study drug and does not have a post-treatment surgical resection, or the surgery is delayed beyond 48 hours of treatment for any reason, the patient will be evaluable for toxicity, but will be inevaluable for all other study endpoints; another patient may be added to accrual.

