6.3.3 Feasibility

To assess feasibility, the rate of successful production, delivery, and administration of the investigational product and subsequent resection will be calculated.

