10.3.3 Exploratory Objectives

To evaluate the Bcl2L12 expression levels and apoptotic markers in the tumor tissue post-treatment, and to evaluate preliminary response (Overall Survival and Progression Free Survival at 2 years, as well as Overall Response Rate) we will describe expression levels and PFS and OS Kaplan-Meier curves corresponding to in study time up to 24 months.

In general, all patients properly included in the study who undergo surgery for tumor removed will be included in the analysis. Thus, an incorrect treatment schedule or drug administration would result in exclusion from the analysis of the tumor accumulation study. All conclusions will be based on all eligible patients. Subanalyses may then be performed on the basis of a subset of patients, excluding those for whom major protocol deviations have been identified. However, these subanalyses may not serve as the basis for drawing conclusions concerning treatment efficacy, and the reasons for excluding patients from the analysis should be clearly reported.

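### Section 10.3.2 gives the four-step feasibility endpoint no defined success, rate or denominator, and sections 4.9 and 10.3.3 may leave out pre-infusion and resection failures

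*Combined protocol and SAP*

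**What the plan says.** The endpoint is defined twice in the same terms. Section 2.2.3: "Feasibility will be calculated as the rate of successful production, delivery, and administration of the investigational product and subsequent resection". Section 6.3.3: "the rate of successful production, delivery, and administration of the investigational product and subsequent resection will be calculated". Neither place gives a denominator.

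The planned analysis is one sentence in section 10.3.2: "To evaluate the feasibility of NU-0129 administration, we will record a) successes/failures, b) number of attempts to administrate nanoparticles".

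Three other statements bear on who is counted:

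- Section 4.9, patients lost before infusion: "If a patient withdraws for any reason after consent or registration but before receiving investigational product, he or she may be replaced".
- Section 4.9, infused patients with no resection or one later than 48 hours: "the patient will be evaluable for toxicity, but will be inevaluable for all other study endpoints".
- Section 10.3.3, on analysis in general: "all patients properly included in the study who undergo surgery for tumor removed will be included in the analysis". Shortly afterwards it adds: "All conclusions will be based on all eligible patients". The Study Summary repeats both statements under Statistical Methodology.

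**The concern.** The endpoint asks whether product can be made, delivered and infused, with resection to follow. A failure at any of the four steps is a feasibility failure. The analysis sentence names only administration, and only in connection with the objective and the count of attempts. Its successes and failures have no stated event, and no rate is formed.

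The population rules make this more than a missing detail. A patient who fails at production or delivery has not been infused, so 4.9 allows replacement if that patient withdraws, and nothing says whether the replaced patient still counts. A patient who fails at resection has been infused, and 4.9 then makes that patient inevaluable for feasibility. Two analysts could both follow the plan and report different figures, and the more convenient figure omits the failures. With 6 to 8 patients, one omission is visible in the result.

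**Working it through.** **1. Is there a plan figure to reproduce?** No. The documents give no expected feasibility rate, target, threshold or failure rate. Section 10.2 bases n = 6, 7 or 8 on recruitment and conduct, and its statement about precision is qualitative.

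**2. Endpoint against analysis**

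| Element | 2.2.3 and 6.3.3 | 10.3.2 |
|---|---|---|
| Summary measure | calculated rate | recorded counts |
| Production | included | not named |
| Delivery | included | not named |
| Administration | included | named |
| Resection | included | not named |
| Definition of success | all four steps | none |
| Denominator | none | none |

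**3. Where failures can drop out**

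- *Before infusion.* Section 4.6 allows up to 14 days from registration to infusion, so a registered patient may never be infused. Section 8.1.6 sets storage limits of 3 hours for vials and 8 hours for prepared solution, and requires vials with extraneous particles to be discarded. Section 4.9 permits replacement and is silent on counting.
- *After infusion.* If 4.9 is applied to feasibility, every infused patient who remains has had a resection within 48 hours. The resection step then succeeds in 100% of them by construction.
- *Analysis set.* The surgery-based set in 10.3.3 would remove both groups, apart from infused patients whose surgery was late. The all-eligible statement would keep registered patients, because registration requires confirmed eligibility (sections 3.0 and 11.3). The text does not say which governs feasibility.

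**4. Size, on assumed counts**

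Let n patients be infused and resected in the window, and let k registered patients fail before infusion. If the k are not counted, the result is n/n. If they are, it is n/(n + k). The overstatement is k/(n + k). Intervals are exact (Clopper-Pearson) two-sided 95%: for x of N, the lower limit is the 2.5% point of Beta(x, N − x + 1) and the upper limit is the 97.5% point of Beta(x + 1, N − x), with the upper limit 1 when x = N.

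| k (assumed) | n = 8 | 95% CI | Overstatement | n = 6 | 95% CI | Overstatement |
|---|---|---|---|---|---|---|
| 0 | 8/8 = 100% | 63.1–100% | 0 | 6/6 = 100% | 54.1–100% | 0 |
| 1 | 8/9 = 88.9% | 51.8–99.7% | 11.1 points | 6/7 = 85.7% | 42.1–99.6% | 14.3 points |
| 2 | 8/10 = 80.0% | 44.4–97.5% | 20.0 points | 6/8 = 75.0% | 34.9–96.8% | 25.0 points |
| 3 | 8/11 = 72.7% | 39.0–94.0% | 27.3 points | 6/9 = 66.7% | 29.9–92.5% | 33.3 points |

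Resection failure alone: if 8 are infused and 1 has no resection in the window, 4.9 leaves 7/7 = 100%, while the four-step rate is 7/8 = 87.5% (47.3–99.7%). With 6 infused the comparison is 5/5 = 100% against 5/6 = 83.3% (35.9–99.6%).

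One failure of each kind: 7/9 = 77.8% (40.0–97.2%) with 8 infused, or 5/7 = 71.4% (29.0–96.3%) with 6 infused.

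**The case against.** A reader might infer that 10.3.2 analyses administration only and that failures before infusion can never reach the result. The documents do not support that reading, for three reasons, all of which stand.

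- The Study Summary uses the phrase "To evaluate the feasibility of NU-0129 administration" for the whole feasibility objective. The successes and failures in 10.3.2 could therefore mean success on the four-step definition. Only the count of attempts is expressly about administration.
- Sections 2.2.3 and 6.3.3 are current text and still promise the full rate. Section 10.3.2 does not revoke them.
- The replacement rule in 4.9 concerns accrual. It does not declare undosed patients inevaluable, and 10.3.3 also points to all eligible patients.

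These reasons do not close the gap. No section gives a denominator, and for resection failures 4.9 is explicit: the patient is inevaluable for an endpoint that includes resection.

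Two further objections limit the size of the point. First, NU-0129 is not made for individual patients. It is supplied as vials of about 0.987 mg (section 8.1.9), so a manufacturing failure might hold up everyone rather than remove one patient here and there. That weakens an illustration built on production failures, although a failure during preparation on the day could still affect a single patient. Second, no threshold or decision depends on the feasibility rate, so any bias affects what is reported and not a go/no-go rule.

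**Conclusion.** The point holds as a gap between endpoint and analysis. The plan defines a four-step rate and does not say how to compute it, and its population rules may remove the failures that the rate should count. The resection part is the firmest, because 4.9 contradicts the endpoint definition directly. The pre-infusion part rests on silence and on conflicting statements about the analysis set, so the most that can be said is that these failures may be left out.

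The size is conditional. With no failures there is no bias. With one to three uncounted pre-infusion failures and 6 to 8 infused patients, a reported 100% would correspond to between 67% and 89%. These counts are assumptions and should not be read as a forecast for this trial. The intervals are wide under every scenario, so an explicit denominator matters more than the precision of the rate.

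**What to change.** Replace the feasibility sentence in 10.3.2 so that it does the following:

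1. Defines success as completing all four steps of 6.3.3, and says whether a resection outside the 8–48 hour window counts as success at the last step.
2. Uses all registered patients as the denominator, including any replaced under 4.9. Patients who consented but were not registered can be listed separately.
3. Reports n/N and the reason for failure at each step, with an exact 95% confidence interval for the overall rate and the number of attempts as a supporting figure.
4. Keeps withdrawals unrelated to product or procedure in the denominator of the main rate, and shows a supporting rate without them.
5. States that the 4.9 evaluability rule and the surgery-based analysis set in 10.3.3 do not apply to feasibility. A matching phrase in 4.9 would remove the contradiction at its source.

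The cost is a short amendment, which needs review and approval under section 11.2. Most of the data should already exist: registration records (11.3), reasons for discontinuation on the eCRF (4.8), the Drug Administration Log (8.1.11) and drug accountability records (8.1.12). None of these is said to record production or delivery failures, so one field for the reason a registered patient was not infused may be needed. The reported feasibility figure may also be less favourable.
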